**Indications for VIG/cidofovir release:**

- Vaccinia Immune Globulin (VIG) and cidofovir are indicated for the treatment of certain serious smallpox vaccine adverse events, including progressive vaccinia, eczema vaccinatum, generalized vaccinia (severe form or if underlying illness), and inadvertent inoculation (if judged to be severe due to the number of lesions, toxicity of affected individual, or significant pain). VIG is recommended as the first line of therapy. Cidofovir may be considered as a secondary treatment, and will only be released by CDC after all inventories of VIG have been exhausted, after a patient fails to improve with VIG treatment, or as a last effort for a patient who is otherwise near death.
- VIG and cidofovir are available for civilians through the CDC under Investigational New Drug (IND) protocols for treatment of specific smallpox vaccine reactions. Based on the anticipated number of adverse events resulting from the planned vaccination program for healthcare workers, CDC's supply of VIG should be adequate.

**Process for obtaining VIG/cidofovir under Investigational New Drug Protocol (IND):**

1. **Contact the South Carolina Department of Health:** Physicians should first contact their State Health Department when seeking consultation for civilian patients experiencing a severe or unexpected adverse event following smallpox vaccination or when requesting VIG or cidofovir.
2. If further consultation is required, or VIG or cidofovir is recommended, the physician will be referred to the **CDC Clinical Information Line (CIL) at 1- [contact]**. The nurses staffing the CIL will take basic information and then expedite the call to the CDC Smallpox Vaccine Adverse Events Clinical Consultation Team. The CDC Clinical Consultation Team will provide in-depth consultation and will facilitate VIG or cidofovir release as appropriate.
3. According to FDA regulations, VIG or cidofovir released from the CDC must be administered according to their investigational new drug protocols (IND). The IND mandates that the treating physician must become a co-investigator. The responsibilities of the co-investigator are primarily to complete follow-up forms describing the clinical status of the patient being treated with VIG and/or cidofovir, including the prompt report of any significant adverse reaction in the recipient. Detailed information on the requirements of the IND will be shipped with the products.

**Shipment of VIG/cidofovir**

- VIG/cidofovir will be shipped by the National Pharmaceutical Stockpile (NPS). The CDC Smallpox Vaccine Adverse Events Clinical Consultation Team will coordinate the shipment of VIG/cidofovir with NPS. The cost of VIG and cidofovir and the cost of shipping will be covered by the U.S. Government. Arrival of shipments should be expected within 12 hours of the approval for release.

## **APPENDIX D: PHONE CONTACT GUIDE**

This form is to be used if a patient does not come back to HCC for follow up visits after the day 141 PROSTVAC-F administration.

**Study ID/Initials:** \_\_\_\_\_ **Date:** \_\_\_\_\_ **Timepoint:** \_\_\_\_\_

- Call conducted (complete information below)
- Patient could not be contacted after \_\_\_\_ attempts.

## 1. Are you experiencing any side effects?

[Document any side effects reported by the subject. Severity to be confirmed by a study-approved investigator. Attribution to done by a study-approved investigator.]

**2. Are you receiving any form of prostate cancer treatment?**

Yes       No      Date treatment was started:

3. What is your most recent PSA value? \_\_\_\_\_ ng/dL

4. **Day 225 and Day 730 only:** May we ask you some quality of life questions?  Yes  No

[If yes – administer the quality of life questionnaires]

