## 7.5 EFFICACY ASSESSMENTS

Efficacy assessments will primarily be performed by measurement of PSA and by physical assessment. Imaging studies (CT scans of the abdomen and pelvis, and bone scans) will be performed at baseline (up to 16 weeks prior to treatment) and at the end of the study (or within the preceding 2 months before end of study). Otherwise, scans will be performed only if clinically indicated for evaluation of relapse or off study. Additional forms of imaging (Prostascint scan, MRI) may be substituted for a CT scan of the abdomen and pelvis if clinically indicated. However, the imaging method used at baseline will be used for follow up scans. Compliance with therapy may be considered a component of the efficacy assessment. Compliance with PROSTVAC-V/F will be monitored at each visit by interviewing the patient and reviewing the infusion center records for administration.

Both primary and secondary efficacy assessment involve measurement of RFS. Recurrence will be defined as the occurrence of any of the following:

- Institution of new prostate cancer therapy
- First detection of a PSA level  $\geq 0.2$  ng/mL (confirmed  $> 30$  days later) after completion of all PROSTVAC V/F vaccine doses
- Development of radiographically-demonstrable metastases
- Death

RFS at two years will be met if a patient has met none of the above criteria two years post-surgery. RFS as a time to event endpoint will be measured as the time in days from surgery to any of the above conditions being met.

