- j. If available: Send 5 thin (5 micron) sections on glass for H+E and IHC staining. These can be sent at any time after consent has been signed.
- k. Lipid panel requires patients to be fasting and can be done any time after informed consent is signed and prior to day 1 agent administration.
- l. HIV, Hep B and Hep C serology screening, unless known negative within previous 2 years prior to registration.
- m. PSA confirming eligibility can be done outside of the 30 day window. However, if PSA confirming eligibility was done greater than 30 days prior to day 1, it should be repeated prior to day 1 agent administration to ensure PSA is < 0.2ng/mL
- n. Day 1 assessments completed within 24 hours of screening assessments do not need to be repeated.
- o. Interim medical history includes any changes to the patient's medical history and/or any clinical changes since the previous clinic visit.
- p. For non-local patients in follow up, all attempts should be made to have subject return to the clinic for all follow up visits, but specifically day 225 and day 703. However, clinical care procedures (PSA, CMP, CBCD, focused physical exam and interim medical history – to include AE assessment and conmed assessment) may be done locally and the records provided. At a minimum, a PSA must be done and results provided to the study team. If a clinic visit is not done during follow up, the study team may conduct a phone interview (using the phone contact guide, Appendix D) in lieu of an clinic visit to assess adverse events, current cancer therapy and PSA level. Quality of life surveys may also be conducted over the phone by the study team if the subject does not return to clinic.
- q. Questionnaires may be mailed to the subject in pre-metered envelope if they are unable to come into the clinic to complete them (ie: due to COVID19 travel restrictions). The subject will complete the questionnaires at home and then mail the completed questionnaires back to the main site in the provided envelope.

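### The fallback phone form asks only about current prostate cancer treatment, so new therapy begun and finished between contacts can be missed and a relapsed man could be scored recurrence-free

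*Combined protocol and SAP*

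**What the plan says.** **The event.** Section 7.5 lists "Institution of new prostate cancer therapy" as one form of recurrence, alongside confirmed PSA rise, radiographic metastases and death. The synopsis does the same. The binary primary endpoint follows: "RFS at two years will be met if a patient has met none of the above criteria two years post-surgery". The event is the start of therapy, whether or not the therapy is still running when the man is next contacted.

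**The fallback contact.** Appendix A note p, written for non-local men in follow-up, prefers a return to clinic. It then adds: "If a clinic visit is not done during follow up, the study team may conduct a phone interview", whose scope is "to assess adverse events, current cancer therapy and PSA level".

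**The form.** Appendix D covers follow-up after the Day 141 dose. Question 2 is "Are you receiving any form of prostate cancer treatment", with yes and no boxes and one further field, "Date treatment was started". Question 3 is "What is your most recent PSA value", with no field for the date of the test or for earlier values. The form has no stop date and no wording that looks back to the last contact. It carries an item for Day 225 and Day 730, so it can be used at the last scheduled contact.

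**The concern.** The endpoint asks whether therapy was ever started. The form asks whether it is being received on the day of the call. The two questions give different answers for a man whose course began and ended since the previous contact: he has relapsed under Section 7.5, yet a truthful answer to question 2 is no.

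The new-therapy limb matters most where the PSA limb is silent. A PSA event needs confirmation more than 30 days later, so a man treated before confirmation is an event only through new therapy.

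A miss by this route can only turn a relapse into a success. It also affects comparability. Section 10.1 says the 243-man historical series behind the 0.60 null counted new therapy as relapse, so under-capture in this trial would favour the vaccine against that benchmark. The time-to-event analyses of RFS draw on the same follow-up information.

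**Working it through.** **1. Can a course fit between two calls?** The Appendix A contacts after the last dose are Days 141, 225, 309, 393, 477, 561, 645 and 730. Successive gaps are 84 days six times, then 85. With the ±7-day window at each end, an 84-day gap runs from 70 to 98 days, and the 85-day gap from 71 to 99. The documents give no length for a course of later treatment. For an assumed course of L days starting at random in a gap of T = 84 days, the share lying wholly inside the gap is (T − L)/T:
- L = 42: 42/84 = 0.50
- L = 56: 28/84 = 0.33

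This is the chance of falling between two calls. It is not the chance of being missed for good, because later contacts can recover the event.

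**2. The plan's own operating characteristics.** Section 10.1 gives a null of 0.60, an alternative of 0.78, a stop at 11 or fewer of 19, rejection at 22 or more of 30, type I error 0.1 and power 0.8. The exact probability of rejection is

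P(reject | p) = Σ over x = 12 to 19 of P(X₁ = x) × P(X₂ ≥ 22 − x), with X₁ ~ Bin(19, p) and X₂ ~ Bin(11, p).

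At p = 0.60 this is 0.0934, and at p = 0.78 it is 0.8007. The stated figures reproduce.

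**3. What missed relapses would do.** Let m be the share of relapsed men scored recurrence-free. The documents give no value for m, so every row with m above zero is an assumption. Under the null, the observed success probability becomes 0.60 + 0.40m. The expected number of relapses among 30 men is 30 × 0.40 = 12, so 12m men are expected to be misclassified. Section 10.1 also states rejection at 24 or more of 30, so both cutoffs are shown with the same interim rule.

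| m (assumed) | Men misclassified (12m) | Observed p | Type I error, ≥22/30 | Type I error, ≥24/30 |
|---|---|---|---|---|
| 0 | 0 | 0.600 | 0.093 | 0.017 |
| 1% | 0.12 | 0.604 | 0.101 | 0.019 |
| 2% | 0.24 | 0.608 | 0.109 | 0.021 |
| 5% | 0.60 | 0.620 | 0.136 | 0.029 |
| 7.5% | 0.90 | 0.630 | 0.162 | 0.037 |

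With the 22/30 cutoff there is little slack below 0.10: about 1% of relapsed men missed uses it up. At the boundary, one misclassified man (21 recorded as 22) changes the decision. With the 24/30 cutoff, type I error stays well under 0.10 across this range.

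**The case against.** The strongest reply is that the call is an optional fallback and other routes can expose the treatment.

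- **Local records.** Note p lets local care supply PSA, laboratory tests, a focused examination, and an interim history that includes adverse events and concomitant medication, with records provided. Note o defines interim history as changes since the previous clinic visit, which is the look-back the phone question lacks.
- **Later contacts.** Note p asks for every effort to bring the man back to clinic, naming Day 225 and a late visit (printed as day 703). The off-study procedures in Section 7.3 include history, PSA, testosterone and scans. A clinic visit after a phone contact can recover an event that the call missed.
- **Other routes.** A PSA result is mandatory. Other anti-cancer therapy is prohibited (Section 6.1) and requires withdrawal (Section 4.7). The man may also simply mention it.

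Much of this stands. A reader might infer that such treatment *is* missed and the man *is* scored a success, or that nothing else done remotely would catch him. The documents do not support either reading. Nor does Section 7.5 make a man with no recorded event a success: it requires that he has met no criterion, so the problem is ascertainment, not the endpoint rule.

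The reply does not close the gap. The local history and records are permitted, not required; only the PSA is the minimum. Question 3 takes only the latest value, which may be uninformative if treatment has lowered it. The withdrawal rule works only once the team knows. The form can also be used at Day 730, when no later scheduled visit remains.

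**Conclusion.** The concern holds as an ascertainment gap confined to follow-up by phone. Question 2 and note p cover current treatment, while the endpoint counts any start of therapy up to two years after surgery. A relapse of this kind can be missed, and any such error favours the vaccine.

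That much rests on the wording alone. The size does not. The documents do not say how many men will be followed by phone, how many relapses will be identified only through new therapy, or how long treatment lasts. The type I error figures are therefore illustrations: 0.101 to 0.136 for 1% to 5% missed with the 22/30 cutoff, and below 0.04 up to 7.5% missed with the 24/30 cutoff. A reader might infer that type I error is in fact inflated above 0.10. That would need a miss rate the documents do not supply, and it depends on which of the two stated cutoffs applies. The change is worth making because it is cheap and protects a component of the primary endpoint.

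**What to change.** - **Appendix D, question 2.** Reword to: *Since your last study contact, have you started or received any prostate cancer treatment, including treatment that is now finished? Type, start date, stop date.*
- **Appendix A, note p.** Replace the reference to current cancer therapy with *any prostate cancer therapy since the last contact*.
- **Records.** When the answer is yes, request the treating clinic's record so that the event and its date are documented.

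The cost is one reworded form question, one calendar footnote, and a records request for men who answer yes. No visit, test or patient is added, and clinical management does not change.
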